20.1 Laboratory trials

Participants will be recruited through standard recruitment methods, including emails, posters, leaflets and other advertising routes to staff and students of LSHTM and other members of the public. Participants will be fully informed before the study and it will be made clear that they can withdraw from the study at any time. Participants will be given and asked to read the Participant Information Sheet (Appendix 1) and Product Information Sheet (Appendix 2) which describes the tests which they will take part in, and a consent form (Appendix 3) which must be signed before the test begins. Because in the laboratory trials all participants will test all products and all concentrations, this study is non-randomised.

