12.2 Secondary Objectives

1. To compare the duration of protection offered by different repellent products using the median Complete Protection Time (mCPT)
2. To compare the effectiveness of protection offered by different repellent products using the median effective dose and median effective time
3. To assess the acceptability of the repellent products tested in the field trials using qualitative data from participants.

13 Trial Design

This is a within-subject, non-masked, trial of the use of commercially available insect repellents against *Musca sorbens*, with two consecutive participant groups in the laboratory and in the field, and a primary endpoint of measuring the protective efficacy of each repellent product.

The trial is within-subject to allow comparison of *M. sorbens* contacts on the same participants both before (control) and after (test) application of the repellent or repellent device. This is to mitigate any possible inter-individual attractiveness effects. Control sampling will be conducted before test sampling, to preclude contamination of the control sampling by the test sampling. For this reason, the trial is not masked.

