13.1 Laboratory trial

In preliminary laboratory clinical trials in London, 17 participants will test all products that have been found to exhibit repellency to *Musca sorbens* in benchmarking laboratory studies. These will be chosen from: DEET (N,N-diethyl-3-methylbenzamide), IR3535 (3-[N-butyl-N-acetyl]-aminopropionic acid ethyl ester), Picaridin (2-(2-hydroxyethyl)-1-piperidinecarboxylic acid 1-methylpropyl ester); PMD (para-Menthane-3,8-diol) or permethrin (m-Phenoxybenzyl)-cis,trans-3-(2,2-dichlorovinyl)-2,2-dimethylcyclopropanecarboxylate). Products tested will be either (1) topical repellents, or (2) in long-lasting, plastic formulations of repellents that can be worn on the body (wearable repellent technologies). The insect repellent synergist Vanillin (4-Hydroxy-3-methoxybenzaldehyde) may be added to the long-lasting plastic formulations, to improve the duration of protection.

As all participants will test all products and all concentrations, this study is non-randomised. The combination of product and product format to be tested will be determined before the study commences. Participants will be asked to place their arm in a cage with 100 *Musca sorbens* flies, and the behaviour of the flies on the surface of the arm and hand will be filmed for ten minutes. This modified arm-in-cage assay has been developed specifically for use with *Musca sorbens*.

There will be a two-stage selection process to determine which repellent products, at which concentration (dose), should be carried forward to the field trial. In the first stage, a single measure of Protective Efficacy (PE) will be used to determine protection, by measuring the duration of fly-arm contact after application of a repellent product (test measurement) relative to that before application of the product (control measurement). By only selecting repellent products/concentrations that protect against at least 30 % of fly contact immediately following application (at time zero), those with little or no effect will be disregarded.

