21.1 Laboratory trials

21.1.1 Test insects

On the day before each test, *Musca sorbens* flies of between one and 14 days post-emergence will be brought into testing room and allowed to acclimatise overnight and for at least 12 hours. Flies will be starved of their sugar and protein source (milk or milk powder) during this time period.

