21.1.3 Topical repellents

21.1.3.1 Protective Efficacy

Consenting participants will be asked to avoid the use of fragranced cosmetic or washing products for 12 hours prior to each laboratory trial. Immediately before testing, the participant's arm will be washed with unscented soap, rinsed with water, rinsed with 70 % ethanol in water, and towel dried. An analytical standard of the repellent will be tested at five incrementally increasing doses up to a maximum of 20 %, each diluted in ethanol.

For the first test, the diluent alone (1.4 ml) will be tested as a control. This will be applied to the participant's arm and allowed to dry for one minute. The participant will then insert his/her arm into a purpose-designed insect cage, with a hole in the top allowing a camera lens to film the upper surface of the hand and arm. The cage will contain 100 test insects, and insect behaviour on the arm will then be filmed for ten minutes. This video footage will retrospectively be analysed for the number of fly contact, and the total duration of fly contact. The participant will be instructed to refrain from moving his/her arm, which will disturb landing flies.

For the test to proceed, there must be five or more fly contacts, with the diluent (control,) in the ten-minute observation period. After this, the participant will remove their arm from the cage, carefully brushing off any flies as they leave. The lowest dose of repellent in ethanol (1.4 ml) will then be applied to the arm and allowed to dry for one minute. The participant will then re-insert his/her arm into the cage with the test insects, and insect behaviour on the arm will again be filmed for ten minutes.

This procedure will be repeated for each incremental dose of the repellent, up to a maximum of 20 % active ingredient. Each dose will be tested serially and without delay. To determine the repellent dose, the doses applied to reach that which was effectively repellent will be summed. If at any point the fly-arm contact rate drops below five in 10 minutes, the test will be stopped. After all repellent doses have been tested, 1.4 ml of the diluent control will be applied to the participant's other arm, and tested again as per the first ten-minute test, in order to verify continued fly contact/landings. If at this point there are less than five fly contacts, the results of the experiment will be discarded.

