21.1.3.2 Persistence

Having established which repellent products are effective at which doses, the persistence of all repellent products at doses achieving at least 30 % protection (at time zero) will be determined. Persistence will be determined using an extended version of the protocol described in 21.1.3.1. Preparation, and control testing, will be conducted in the same manner, then the repellent products at the appropriate dose will be applied and tested for ten minutes as previously, and the observation will be repeated every hour for six hours (Figure 5). After testing, the participant will be given access to washing facilities to wash off the topical repellent. This data will allow calculation of the Median Protection Time/Effective Dose (ET_{50} and ED_{50}). To determine the Median Complete Protection time (mCPT), the same protocol will be used however the first test sampling period will be extended until the first fly-arm contact.

[figure not shown]

Figure 5. Timescale for repellency complete protection time (CPT), and median protection time, testing in the laboratory.

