21.1.4 Wearable repellent devices

The protection afforded by wearable repellent devices against *M. sorbens* contacts, formulated at the effective dose determined in 21.1.3.1, will be measured (protective efficacy) and the persistence of this effect determined. Wearable repellent devices will be tested in an extended version of the protocol described in 21.1.3.2. Preparation and control testing will be conducted in the same manner but without the application of any diluent prior to the control test. The participant will then be given the wearable repellent device and asked to put it on (i.e. wear the necklace or neckband around their wrist), and a ten-minute test period will be conducted as previously described (21.1.3.1). After this, the observation will be repeated every hour for six hours. These procedures (control then tests over six hours) will be repeated every week for four weeks, and each timepoint participants will wear the repellent devices that they wore in the initial test at the first timepoint (Figure 6).

[figure not shown]

Figure 6. Timescale for wearable repellent device testing in the laboratory.

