22.4 Burden associated with participation

22.4.1 Laboratory trials

Participants will be required to make repeat visits to the LSHTM testing facility, to test each product and product formulation. During visits, they will be required to sit still for ten-minute observation periods, allowing flies to crawl freely over their forearm and hand.

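### Laboratory product order is neither specified nor balanced and no session term is planned, so session trends can bias the product comparisons, mCPT above all

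*Combined protocol and SAP*

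**What the plan says.** Section 20.1 states: "Because in the laboratory trials all participants will test all products and all concentrations, this study is non-randomised". Section 13.1 gives the same reason: "As all participants will test all products and all concentrations, this study is non-randomised". No section says in which order products are tested, whether the order is the same for everyone, or whether it is balanced.

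Testing is spread over time. Section 22.4.1 says "Participants will be required to make repeat visits to the LSHTM testing facility, to test each product and product formulation", and the timeline in section 30 gives the laboratory work two months. Test conditions may vary: section 21.1.1 says "flies of between one and 14 days post-emergence will be brought into testing room", and section 21.1.2 allows 20-27 °C and 20-50 % relative humidity.

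Each session has its own control:
- Stage 1 topicals (21.1.3.1): "For the first test, the diluent alone (1.4 ml) will be tested as a control".
- Persistence (21.1.3.2): "Preparation, and control testing, will be conducted in the same manner".
- Devices (21.1.4): "These procedures (control then tests over six hours) will be repeated every week for four weeks".

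PE is computed relative to that control (26.3.1). Complete protection time is the elapsed time to the first landing, summarised by Kaplan-Meier (26.3.2). The ED50/ET50 model has terms for dose and time since treatment only (26.3.3).

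The second of the secondary objectives in section 12.2 reads "To compare the effectiveness of protection offered by different repellent products using the median effective dose and median effective time". The first compares products on mCPT. Under section 13.1, persistence estimates from stage 2 decide which products and concentrations go to the field.

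**The concern.** The stated reason for not randomising concerns who gets which product. In a design where each person tests several products on different visits, the open question is which product comes when, and the plan does not answer it. Anything that changes from visit to visit and alters the response to a repellent can then be read as a difference between products.

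The product comparisons in section 12.2 are at stake, and with them the choice of field arms. Section 13.2 allows at most four product groups, while Tables 1 and 2 list three topical and five wearable actives. If more than four candidates pass stage 1, they will have to be compared with one another. Bias from a shared order does not shrink with more participants and cannot be removed afterwards.

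**Working it through.** **1. The plan's own figure.** Section 19.1 uses an SD of PE of 30 %, a margin of ±15 % and 5 % loss. With an inferred 95 % level, n = (1.96 × 30/15)² = 15.37, rounded up to 16. Then 16/0.95 = 16.8, rounded up to 17. The stated 16 and 17 reproduce. This calculation concerns the precision of one product's PE and does not bear on order.

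**2. When product and session can be separated.** Take 17 participants and, as an assumption, five products in five sessions. A model with participant, product and session effects has 17 + 4 + 4 = 25 free parameters.
- One common order: the design matrix has rank 21 (17 + 4). Product and session are the same variable.
- Order randomised for each participant: rank 25. Both effects can be estimated.

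**3. Which outcomes a session trend reaches.** PE is p = 100 × (C − T)/C. If a session multiplies fly activity by k, then (kC − kT)/(kC) = (C − T)/C, so k cancels. ED50 and ET50 are fitted to p and share this protection. Only a change in T relative to C gets through. Complete protection time has no C in it, so k passes straight into it.

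**4. Illustrative size.** The trend sizes are assumptions, and the documents give none. All products are truly equal.

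The first case is activity falling 10 % per session, with time to first landing inversely proportional to activity. The last-to-first mCPT ratio under a common order is 1/0.9^(m−1) for m products:
- m = 3: 1/0.81 = 1.23.
- m = 5: 1/0.6561 = 1.52.

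The second case is PE itself falling 5 points per session. The last-minus-first difference is −5 × (m − 1), that is −10 points for m = 3 and −20 points for m = 5.

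A simulation (17 participants, five products, true PE 50 %, SD 30, 4,000 runs) agrees:

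| Assumed trend per session | Order | PE, last minus first | mCPT, last/first |
|---|---|---|---|
| Activity −10 % | common | −0.1 points | 1.53 |
| Activity −10 % | randomised | −0.1 points | 1.02 |
| PE −5 points | common | −20.3 points | 1.02 |
| PE −5 points | randomised | −0.2 points | 1.00 |

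**5. Scale for the PE figures.** The ±15 of section 19.1 is for a single product. For a difference between two products in 16 people the margin is 1.96 × 30 × √(2(1 − ρ))/√16 = 14.7 × √(2(1 − ρ)). The within-person correlation ρ is not given. At ρ = 0 the margin is 20.8 points and at ρ = 0.5 it is 14.7. A drift of 10 to 20 points would be of similar size.

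**The case against.** A reader might infer that any session trend is fully confounded with product. The documents do not support that, for two reasons. Full aliasing needs one common order, and none is stated. In section 20.1 the word non-randomised most naturally describes allocation of people, and an unrandomised order that varied between people would be only partly confounded. Nor does every trend matter: the same-session control removes proportional changes in activity from PE, ED50 and ET50.

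The sources of drift are also uncertain. Flies are brought in the day before each test, so nothing implies that their age moves with session number. Section 26.1.1 records fly age, sex and number, date, temperature and humidity. Laboratory video is scored retrospectively, and nothing ties scoring order to visit order.

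The consequences are limited as well. Stage 1 applies an absolute 30 % PE threshold against the product's own control and is not a contrast between products. Stage 2 has no stated ranking rule. The primary objective is a before-after comparison. Section 16.2.2 leaves the Phase 3 decision to field results, and field participants are randomised (20.2).

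All of this stands, and it narrows the point without removing it. Product comparisons are still planned, final selection still rests on stage 2, and mCPT lacks the protection that PE has. Recorded covariates help only where product and session are not aliased.

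**Conclusion.** That everyone tests everything is not a reason to leave product order unrandomised. As written, the plan does not protect the between-product comparisons, or the stage 2 selection that draws on them, against session trends that escape the same-session control. mCPT is exposed even to a simple change in fly activity. PE, ED50 and ET50 are exposed only to a change in relative protection.

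The size of any bias cannot be derived from the documents. The mCPT ratios of 1.23 to 1.52 and the PE differences of 10 to 20 points rest on assumed trends, an assumed three to five products and one common order. They show what the design would let through and are not a forecast. The documents do not show that any product comparison is biased. The point is a low-cost improvement that should be made before testing starts, and it leaves the primary before-after objective and the sample size as they are.

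**What to change.** State in sections 13.1 and 20.1 that each participant receives a randomised or approximately balanced product order, for example one built from Latin squares. Generate it separately for stage 1 topicals, stage 2 topicals and wearable devices. One sequence across all of them is not possible, because device dose follows the topical results (21.1.4) and the stage 2 set follows stage 1 (13.1). Keep the plan's dose order within a product.

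In section 26.3, add session number and participant to the between-product comparisons. For time to first landing, a survival regression with these terms can sit beside the Kaplan-Meier medians. If an order scheme already exists, describing it and adding the session term would be enough.

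The cost is a schedule list. All products in a stage must be ready at its start, and several will be handled in the same week. Balance is only approximate with 17 people: 17 = 5 × 3 + 2 for three products, and 3 × 5 + 2 for five. The sample size does not change.

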20.2 Field trials

Prior to approaching members of the communities in which we wish to work there will be initial dialogues with the community leaders and local health officials to introduce the purpose and nature of the research project. Following this, participants will be recruited by visiting households in the study site that are home to children in the correct age bracket. Information about the study will be shared with potential participants by members of the field research team, who have previous experience in the participant information and consenting processes. During the visit, participants will be provided with Information Sheets (Appendices 4 and 5), a Product Information Sheet (Appendix 6) and Informed Consent and Assent forms (Appendix 7). Assent will be sought from the participant, and consent from the primary caregiver. This will be in Afaan Oromo, the

regional language. This will be read to those who are unable read. After verbal explanation of the relevant sections of the Information Leaflet and having the opportunity to ask questions, informed consent will be gained and evidenced by a signature or thumbprint signature (deemed acceptable locally due to high rates of illiteracy), in the presence of the study team and independent witness.

Eligible participants will be randomised equally between the topical repellents and wearable repellent devices found to be protective in laboratory clinical trials, and a control group receiving no intervention.

21 Study procedures

This clinical trial encompasses a series of laboratory studies, designed to determine which of a number of commercially available repellents provide protection against laboratory-reared *Musca sorbens* fly contact, followed by a field trial testing the protection afforded by these repellents and wearable repellent devices, from fly contact by wild *M. sorbens* on children aged three to 12 years. In the field trials, the acceptability of these products to the end-users (both children and their caregivers) will be assessed.

Prior to both trials, preliminary benchmarking laboratory studies will be conducted to determine which of five repellent actives will be studied in the clinical trials.

21.1 Laboratory trials

21.1.1 Test insects

On the day before each test, *Musca sorbens* flies of between one and 14 days post-emergence will be brought into testing room and allowed to acclimatise overnight and for at least 12 hours. Flies will be starved of their sugar and protein source (milk or milk powder) during this time period.

21.1.2 Testing room

The temperature and humidity in the room will be monitored and recorded for the duration of the study. Room temperature will be maintained at 20-27°C, and relative humidity (RH) at 20-50 %, however, it has been noted in insect rearing that *Musca sorbens* are minimally affected by changes in temperature and humidity. All tests will be conducted in the diel phase between 09:00 and 17:00.

21.1.3 Topical repellents

21.1.3.1 Protective Efficacy

Consenting participants will be asked to avoid the use of fragranced cosmetic or washing products for 12 hours prior to each laboratory trial. Immediately before testing, the participant's arm will be washed with unscented soap, rinsed with water, rinsed with 70 % ethanol in water, and towel dried. An analytical standard of the repellent will be tested at five incrementally increasing doses up to a maximum of 20 %, each diluted in ethanol.

For the first test, the diluent alone (1.4 ml) will be tested as a control. This will be applied to the participant's arm and allowed to dry for one minute. The participant will then insert his/her arm into a purpose-designed insect cage, with a hole in the top allowing a camera lens to film the upper surface of the hand and arm. The cage will contain 100 test insects, and insect behaviour on the arm will then be filmed for ten minutes. This video footage will retrospectively be analysed for the number of fly contact, and the total duration of fly contact. The participant will be instructed to refrain from moving his/her arm, which will disturb landing flies.

For the test to proceed, there must be five or more fly contacts, with the diluent (control,) in the ten-minute observation period. After this, the participant will remove their arm from the cage, carefully brushing off any flies as they leave. The lowest dose of repellent in ethanol (1.4 ml) will then be applied to the arm and allowed to dry for one minute. The participant will then re-insert his/her arm into the cage with the test insects, and insect behaviour on the arm will again be filmed for ten minutes.

This procedure will be repeated for each incremental dose of the repellent, up to a maximum of 20 % active ingredient. Each dose will be tested serially and without delay. To determine the repellent dose, the doses applied to reach that which was effectively repellent will be summed. If at any point the fly-arm contact rate drops below five in 10 minutes, the test will be stopped. After all repellent doses have been tested, 1.4 ml of the diluent control will be applied to the participant's other arm, and tested again as per the first ten-minute test, in order to verify continued fly contact/landings. If at this point there are less than five fly contacts, the results of the experiment will be discarded.

For a repellent product to be carried forward to the next phase of testing, a protective efficacy of 30 % is required. While 50 % protection is often used as a benchmark for repellent testing, the total proportion of *Musca sorbens* flies in endemic areas and carrying Ct has previously been estimated as 15 % (29). Therefore, it is plausible that reductions in fly-eye contacts of less than 50 % could still have a significant effect on the transmission capability of this vector.

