16.2.1 Laboratory trials application rate

The arm is an estimated 9 % of the adult body surface area (BSA), therefore the forearm and hand can be considered to be 4.5 %. With the average adult BSA of 19,000 cm², the surface area of the forearm can be taken to be 855 cm². As such, 1.4 ml of solution will be applied to the forearm at the appropriate concentration, never exceeding 20 %.

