16.2.2 Field trials application rate

Topical repellent will be applied to a circular area on the cheek. An average diameter of 6 cm would give a surface area of 28.3 cm². As such, 0.05 ml (50 µL) of product will be applied to each cheek at the appropriate concentration, never exceeding 20 %. Topical repellents will be applied at least 3 cm (three finger-breadths) below the eye and positioned away from the nose and mouth.

Due to the differences in surface area under observation in the laboratory and field trials, with greater skin surface areas in the former (application on the arm) leading to greater amounts of active ingredient being applied, there is a risk that efficacy in the laboratory will be greater than that experienced in the field. However, it should be emphasised that the aim of the laboratory trials is to inform which repellents can be taken into the field trial for testing, as this is the context in which such a product would be used. Therefore, while both studies are merited, the Protective Efficacy and other outcome measures as calculated in the field trial will be those that are used to inform inclusion of repellents as a fly-control intervention in the Stronger-SAFE Phase 3 RCT.

17 Study outcomes

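### Stage 1 measures protective efficacy on an accumulated deposit, stage 2 and the field apply a dose once, and the plan never says whether the dose carried forward is the step concentration or the sum

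*Combined protocol and SAP*

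**What the plan says.** **Stage 1 (Section 21.1.3.1).** The dose series is described as: "An analytical standard of the repellent will be tested at five incrementally increasing doses up to a maximum of 20 %, each diluted in ethanol". After the diluent control, the first repellent step is: "The lowest dose of repellent in ethanol (1.4 ml) will then be applied to the arm and allowed to dry for one minute". The same is done for each higher dose, and "Each dose will be tested serially and without delay". The arm is washed before testing, but no wash or removal between doses is described. The dose is then credited in this way: "To determine the repellent dose, the doses applied to reach that which was effectively repellent will be summed". Testing stops early if contacts fall below five in ten minutes. Products and concentrations go forward if PE at time zero is at least 30 % (Sections 13.1 and 21.1.3.1).

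**Application rule for laboratory trials (Section 16.2.1).** "1.4 ml of solution will be applied to the forearm at the appropriate concentration, never exceeding 20" per cent.

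**Stage 2 (Section 21.1.3.2).** After the control test, "then the repellent products at the appropriate dose will be applied and tested for ten minutes as previously", with hourly observation for six hours. This section does not repeat the 20 % cap, but Section 16.2.1 covers laboratory trials generally.

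**Field (Section 16.2.2).** A volume of 0.05 ml "will be applied to each cheek at the appropriate concentration, never exceeding 20" per cent.

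**Other users of the stage 1 result.** Section 21.1.4 formulates the wearable devices at the effective dose found in stage 1. Section 23 allows a lower topical dose to be substituted in the field if that dose gave at least 30 % PE.

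**The concern.** PE is a property of what is on the skin when it is measured. At any stage 1 step after the first, that is the current dose plus whatever remains of the earlier ones. The plan recognises this by summing. Stage 2 and the field then apply something once, and the plan does not define it as the step or the sum. Each reading leaves a gap.

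- **Sum.** If the series reaches 20 %, the sum at that step exceeds 20 % whatever the spacing, because the four earlier doses are positive. One 1.4 ml application at no more than 20 % cannot deliver it.
- **Step concentration.** Every stage 1 PE after the first step belongs to a larger deposit than the one carried forward.

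Either way, the 30 % criterion can credit a dose with protection measured on more product than will be applied later. Weak products are the most exposed: a strong product may stop the series early under the five-contact rule, while a borderline one continues to the steps where most has accumulated. The same uncertainty passes to the device formulation and to the lower-dose substitution.

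**Working it through.** **Plan's own figures.**

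- Forearm: 0.045 × 19,000 = 855 cm². At 1 ml per 600 cm², 855 / 600 = 1.425 ml, stated as 1.4 ml.
- Cheek: π × 3² = 28.3 cm², and 28.3 / 600 = 0.047 ml, stated as 0.05 ml.
- Two cheeks at 20 %, taken as 200 mg/ml: 2 × 0.0471 × 200 = 18.85 mg, as in Section 22.2.1. This confirms the reading of 20 % as 200 mg/ml.

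**One laboratory application at the cap.** 1.4 ml × 200 mg/ml = 280 mg, and 280 / 855 = 0.327 mg/cm².

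**Accumulated deposit at a 20 % top step.** The documents give five steps and the maximum but not the spacing, so four spacings are assumed. Full retention between steps is also assumed, which makes each ratio an upper bound for its spacing.

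Deposit = (sum of step concentrations) × 1.4 ml / 855 cm².

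| Assumed spacing | Steps (%) | Sum (%) | mg | mg/cm² | Ratio to one 20 % application |
|---|---|---|---|---|---|
| Tenfold | 0.002, 0.02, 0.2, 2, 20 | 22.2 | 311 | 0.364 | 1.11 |
| Threefold | 0.25, 0.74, 2.2, 6.7, 20 | 29.9 | 418 | 0.489 | 1.49 |
| Twofold | 1.25, 2.5, 5, 10, 20 | 38.75 | 542.5 | 0.635 | 1.94 |
| Equal | 4, 8, 12, 16, 20 | 60 | 840 | 0.982 | 3.00 |

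**If the sum is carried forward.** What matters is the step at which the sum first exceeds 20 %. With equal steps this is the third (4 + 8 + 12 = 24). With the other spacings it is only the fifth; the twofold sum at step four is 1.25 + 2.5 + 5 + 10 = 18.75.

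**If the step concentration is carried forward.** The ratio of deposit to step dose is 1 at the first step. From the second to the fifth it runs from 1.5 to 3.0 (equal), 1.5 to 1.94 (twofold), 1.33 to 1.49 (threefold) and is about 1.1 throughout (tenfold).

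**Effect on a borderline product.** Suppose PE is exactly 30 % at the top step and follows a logit in ln dose with slope *b*. Then

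PE after one 20 % application = expit(logit(0.30) − *b* × ln(ratio)).

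Example, equal steps and *b* = 1: the odds are 0.30 / 0.70 = 0.4286; divided by 3.0 they become 0.1429; PE = 0.1429 / 1.1429 = 12.5 %.

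| Spacing | *b* = 0.5 | *b* = 1 |
|---|---|---|
| Tenfold | 28.9 % | 27.8 % |
| Threefold | 26.0 % | 22.3 % |
| Twofold | 23.5 % | 18.1 % |
| Equal | 19.8 % | 12.5 % |

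The slopes are assumed; the documents give no dose-response figure.

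**The case against.** The strongest reply is that the plan counts two different quantities and both can hold. Section 21.1.3.1 counts the total deposited in a serial assay, and Sections 16.2.1 and 16.2.2 limit the concentration of an application. Summing is sound accounting. Stage 1 is only a coarse screen to discard products with little or no effect, final selection follows stage 2, and stage 2 measures PE again at time zero after one application. Section 16.2.2 already warns that laboratory efficacy may exceed field efficacy.

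Much of this stands. Summing is not the error, and stage 2 produces the reading that would expose a wrongly admitted product. But no 30 % criterion is attached to that reading: Section 13.1 describes final selection in terms of persistence. The caution in Section 16.2.2 is about treated area, not accumulation. It might also be said that the 20 % maximum in stage 1 is a cumulative total, which would remove the excess over the cap. Section 16.2.1 attaches the limit to the concentration of the applied volume, so the per-application reading is the plain one.

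A reader might infer several stronger points that the documents do not support.

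- **That the credited sum always exceeds 20 %.** Only doses up to the effective one are summed.
- **That the excess is two- to threefold.** That covers twofold and equal steps only; wider spacing gives 1.1 to 1.5.
- **That the dose term in Equation 2 is distorted by the same factor.** Section 26.3.3 places the ED50 and ET50 calculation in stage 2 and uses the dose applied. Nothing there brings in the stage 1 sum.
- **That selected products will underperform.** They may, if they first met the criterion at a late step.

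**Conclusion.** The point holds in a limited form. The plan leaves undefined which stage 1 dose is carried forward, and under either reading a product or dose can meet the 30 % criterion on a deposit that the later single application does not reproduce.

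At a 20 % top step the excess is about 1.1 to 3.0 times. For a PE of exactly 30 % there, the single-application equivalent runs from about 29 % down to 12.5 %. These figures rest on assumed spacing, full retention and a logit slope of 0.5 to 1 per ln dose, and they describe the borderline case only. Products effective at the first step are unaffected. If the sum is meant, so are those whose sum is 20 % or less.

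The field PE estimate is not biased, because it is measured on what was applied in the field, and no sample size depends on this point. What is at risk is the choice of what reaches the field: a weak topical product or dose, a device formulated from that result, or a lower-dose substitution justified by it.

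**What to change.** 1. Reconcile Sections 16.2.1, 16.2.2, 21.1.3.1, 21.1.3.2, 21.1.4 and 23 on whether the dose carried forward from stage 1 is the step concentration or the summed amount. Which dose is right is for the trial team; this review takes no position on it.
2. Before final selection for the field, check the protocol's own 30 % criterion against the stage 2 time-zero PE, which is already collected after a single application.

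The cost is protocol wording and one extra check, with no new participants, visits or measurements. The downside is that some products or doses may be dropped after stage 2.
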